6.2 Inclusion Criteria

To participate in this study, the potential participant **must meet** all of the following criteria:

1. Previously enrolled in the NTMT-01 or NTMT-02 protocol and received the NT-501 implant and/or underwent a Sham procedure.
2. Participant must be offered sufficient opportunity to review and to understand the informed consent form, agree to the form's contents and provide written informed consent.

6.3 Exclusion Criteria

There are no Exclusion Criteria.

6.4 Study Procedures

All study procedures will be carried out for both eyes at each visit. This will include both the study eye(s) and the fellow eye as applicable.

6.5 Concomitant Medications and Procedures

Any concomitant medications a participant is receiving at the start of the study or given for any reason during the study must be recorded in the source document, including start and stop dates and indication information. Recording of concomitant medications on the Case Report Forms (CRFs) must be done according to the instructions provided in the study Manual of Procedures (MOP). In addition, all ocular and non-ocular procedures must also be recorded in the Concurrent Procedures source document.

6.6 Prohibited Medications

Anti-herpetic nucleoside analogs (such as Acyclovir, Valaciclovir, Penciclovir and Famciclovir) or anti-cytomegaloviral nucleoside analogs (such as Ganciclovir or Foscarnet) are prohibited unless required for the safety of the participant and the infection is not expected to be self-limited without treatment. If used, these agents should only be used for the shortest possible duration. When possible, the sponsor, Neurotech, should be consulted prior to initiating treatment. Anti-influenza neuraminidase inhibitors (such as Zanamivir, Oseltamivir) or other anti-influenza medications (such as Arbidol, Amantadine, Rimantadine) are permissible, if clinically indicated.

6.7 Masking

For participants in Cohort 2 there are different levels of masking within the study. The site staff refractionist, visual acuity examiner and photographers/imagers must remain masked to treatment assignment (NT-501 implant or sham procedure) for all visits. The Ophthalmologist, Surgeon and Clinic Coordinator will be unmasked to treatment assignment.

To ensure that the refractionist, visual acuity examiner and photographers/imagers remain masked to the randomized assignment, the Ophthalmologist, Surgeon and Clinic Coordinator are not to discuss the treatment received with the refractionist, visual acuity examiner and photographers/imagers.

All personnel in the Central Image Reading Center will be masked to whether the participant received the NT-501 implant or sham in a study eye(s).

Masking will remain as described above until all 66 participants in the NTMT-02 protocol have completed their original NTMT-02 Protocol Month 24 visit and data analysis has been completed. At that time, the Principal Investigators will be informed by the Sponsor that they

may unmask the participants. They may choose to do this at the participants' next scheduled visit or in a personalized communication to the participant. The sites will notify the Coordinating Center of the unmasking as outlined in the Manual of Procedures.

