6.8 Exam Requirements

The following are examinations to be performed at the times indicated in Appendix 1.

1. Informed Consent and Eligibility Criteria Review
2. Demographics and Participant Contact Information Review
3. Medical/Ophthalmic History Review (carried over from NTMT-01 or NTMT-02)
 - Adverse events noted during the NTMT-02 and NTMT-01 study period and up to the first Extension Study visit will be added as Medical/Ophthalmic History as applicable.
4. Adverse Event Assessment (from the date of the NTMT-01/02 Extension Study consent)
5. Concomitant Medications
6. Complete Ophthalmic Examination including:
 - Manifest refraction
 - BCVA (This test will be performed by a masked certified technician)
 - Goldmann applanation tonometry
 - Slit lamp biomicroscopy
 - Dilated fundus examination
 - Implant site clinical examination
7. Ophthalmic Assessments including:
 - Microperimetry
 - Spectral Domain Optical Coherence Tomography (SD-OCT)
 - Fundus Autofluorescence imaging
 - Digital Color Fundus photographs

- Adaptive Optics Scanning Laser Ophthalmoscopy (AOSLO), in selected participants
 - Participants who underwent AOSLO for NTMT-02 will undergo a separate consent process at the AOSLO Center if they agree to continue participating.

8. Reading Speed –NTMT-02 (Cohort 2) participants only

- Monocular and binocular reading speed will be assessed using IReST cards. Reading speed will be used to document the participant's functional status with an important everyday visual task.

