8.6 Data Quality Assurance

A Coordinating Center will have the primary responsibility for assuring that the quality of the data collected and reported in the study are of consistently high quality. Many factors contribute to the quality of the data, from the design and procedures of the trial to the analytic methods employed. The Coordinating Center works with the Reading Center on the design and implementation of a quality assurance program for grading images collected as part of the study.

The major quality assurance features of the study are:

- Standard data collection forms and procedures;
- Common protocol for eligibility, examination and follow-up of all participants in all clinical centers;
- **MASKED** assessment of the primary outcome measure and secondary outcome measures;
- Central masked grading of study images;
- Data entry into the study database and the Clinical Centers;
- Central, computer driven data editing for missing, invalid and suspect responses;
- Regular reporting of performance of all Clinical Centers;
- Monitoring visits to all Clinical Centers; and
- Certification of clinic staff and of imaging equipment.

9 Human Participant Protection

All participants will receive a verbal explanation from the Principal Investigator or his/her appropriate designee in terms suited to their comprehension of the purposes, procedures and potential risks of the study. In the opinion of the Principal Investigator or designee, the participants must be capable of comprehending the contents of the informed consent and able to sign an informed consent form, which must be obtained prior to enrollment. The participants will have an opportunity to review the consent form carefully and ask questions regarding this

study prior to signing, and they will be informed that they may withdraw from the study at any time without prejudice to themselves.

The participants' names will not appear on any of the data forms reported to the Coordinating Center. Participants will be identified by a study number. The date of birth of each participant will be collected in the data system. The information collected will remain confidential.

10 Study Risks

There are risks associated with the diagnostic procedures required for participants in this study. However, these are all standard procedures that are performed as part of a normal eye and medical exam. Some of the discomforts associated with the ocular exam include the following:

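### Section 6.7 can be read as ending Cohort 2 assessor masking after the NTMT-02 Month 24 analysis, and no section names the reading-speed examiner as masked

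*Combined protocol and SAP*

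**What the plan says.** Section 6.7 (Combined protocol and SAP) sets the masking rules for Cohort 2. The refractionist, the acuity examiner and the imaging staff "must remain masked to treatment assignment (NT-501 implant or sham procedure) for all visits". The ophthalmologist, surgeon and coordinator know the assignment and "are not to discuss the treatment received with the refractionist, visual acuity examiner and photographers/imagers". For the reading center, "All personnel in the Central Image Reading Center will be masked".

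The last paragraph of 6.7 then reads: "Masking will remain as described above until all 66 participants in the NTMT-02 protocol have completed their original NTMT-02 Protocol Month 24 visit", with completion of the data analysis as a further condition. After that point the investigators are told that they "may unmask the participants". The rest of the paragraph covers how participants are told and how sites report it.

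Two other sections bear on the point. Section 6.8 says of BCVA: "This test will be performed by a masked certified technician". It ties its examinations to the Appendix 1 schedule, so this applies at all four extension visits. Of reading speed it says only: "Monocular and binocular reading speed will be assessed using IReST cards". Section 8.6 lists "Central masked grading of study images" among the quality features, together with masked assessment of primary and secondary outcome measures.

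**The concern.** The last paragraph of 6.7 refers back to masking already described, and no participant masking is described before it in that section. Taken literally, the sentence puts an end date on the assessor and reading-center masking that the same section has just required at every visit. A site could follow either rule and claim to be following the protocol.

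Every Cohort 2 efficacy outcome is measured at Month 36 or later (6.1.2), and section 8.2 compares the outcomes between treatment groups. Once participants may know their assignment, masked assessment is the main protection left for those comparisons. By the nature of the tests, the BCVA, microperimetry and reading-speed outcomes depend on the participant's responses to an examiner. The ellipsoid-zone outcomes depend on image graders, whom the literal reading would also release.

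The second gap does not depend on how 6.7 is read. Reading speed is a Cohort 2 efficacy outcome, yet no section says that the person who runs the test is masked.

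Cohort 1 is open label and is not affected.

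**Working it through.** The plan gives no figure to reproduce. The check compares the text, counts outcomes and works through the timing.

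**1. What the last paragraph of 6.7 can refer to.** Three protections stand before it: masked site assessors, the no-discussion rule for unmasked staff, and the masked reading center. Participant masking is implied by the single-masked label in the Study Summary and section 5, but it is not described in 6.7 before the cutoff. The literal object of the cutoff is therefore assessor and reading-center masking.

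**2. What points the other way.**
- The only action that follows the cutoff concerns participants.
- Nothing authorises telling assessors or graders the assignment.
- Section 6.8 places a masked BCVA technician at Months 36, 48, 60 and 72.
- Section 8.6 lists masked central grading.

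**3. Masking by outcome (6.1.2 against 6.7).**

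| Outcomes | Number | Masked role named? |
|---|---|---|
| Ellipsoid-zone change; 35% increase | 2 | Yes: imaging staff, reading center |
| BCVA change; 15-letter loss; 10-letter loss | 3 | Yes: refractionist, acuity examiner |
| Retinal sensitivity | 1 | Arguable |
| Reading speed | 1 | No |

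The total is 2 + 3 + 1 + 1 = 7. Microperimetry is arguable because 6.8 lists it with the imaging tests, while Appendix 1 lists it with BCVA among the tests done before dilation.

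**4. Timing under the literal reading.** Let A be the NTMT-02 accrual time and L the time from the last Month 24 visit to the end of the analysis, in months. The documents give neither. With the first surgery as time zero, the cutoff falls at A + 24 + L. A participant operated on at time u, with 0 ≤ u ≤ A, has extension visits at u + 36 + 12k, for k = 0 to 3.

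- First participant (u = 0): visit k follows the cutoff if 36 + 12k > A + 24 + L, that is, if A + L < 12 + 12k.
- So all Month 36 visits follow the cutoff if A + L < 12. For Months 48, 60 and 72 the limits are 24, 36 and 48.
- Last participant (u = A): all four visits follow the cutoff if A + 36 > A + 24 + L, that is, if L < 12.
- These are nominal dates. Extension visits at the early edge of the one-month window, with Month 24 on its nominal date, lower the four limits to 11, 23, 35 and 47.

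Under the participants-only reading, the cutoff removes assessor masking from no visit, whatever A and L are.

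**The case against.** The strongest reply is that 6.7 has a clear best reading. This is an extension protocol whose visits start at Month 36, so a rule that assessors stay masked at every visit would be largely or wholly empty if the cutoff ended it. By the timing above, it would be wholly empty if A + L were below 12 months. One loose back-reference would have to override specific statements in 6.7, 6.8 and 8.6. That argument stands: the participants-only reading is the better one. It does not remove the need for a correction, because the protocol never says that assessors stay masked after the cutoff.

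On reading speed, the reply is that 8.6 promises masked assessment of primary and secondary outcomes in general. The extension labels no outcome as either. The Study Summary takes the Cohort 2 outcomes from the NTMT-02 protocol, which may carry those labels, and the Manual of Procedures may name the examiner. Neither was available. This limits the point to what the protocol itself states. For microperimetry the reply has more force: the Appendix 1 heading groups tests by pupil state rather than by examiner, so it is weak evidence that imaging staff do not run the test.

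A reader might infer that the protocol plans to unmask assessors, or that reading speed and microperimetry will be done by unmasked staff. The documents support neither. They leave the first open by faulty wording and the second by silence.

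**Conclusion.** The point holds as a conflict in the wording of 6.7 together with a separate omission. The literal text lets sites end assessor masking for some or all of the Month 36 to 72 comparisons. The likely intent is to unmask participants only.

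The outcome count can be stated: five of seven Cohort 2 outcomes rest on roles named as masked, one is arguable, and one has no named masked examiner. The share of visits after the cutoff cannot be stated, because accrual and analysis times are not given. It is also not a measure of bias. A reader might infer that a large part of the follow-up is unprotected, but under the better reading the cutoff leaves no visit without assessor masking.

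The correction is worth making because it removes a real risk of assessment bias at any site that follows the literal text or uses an unmasked reading-speed examiner. Confidence is moderate, given the two documents not available.

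**What to change.** Revise section 6.7 as follows:

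- Reword the last paragraph so that the Month 24 cutoff applies to participants only.
- State that the refractionist, the acuity examiner, the imaging staff and the reading center stay masked through Month 72 to each study eye's original NTMT-02 assignment. Using the original assignment keeps the rule defined if the section 5 provision for sham-only participants is used.
- Add the reading-speed and microperimetry examiners to the masked list, using existing masked staff where the site has them.

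An optional addition is to ask unmasked participants not to reveal their assignment to these staff. The present no-discussion rule binds only the ophthalmologist, surgeon and coordinator.

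The cost is one paragraph, and sites keep the split between masked and unmasked staff through Month 72. The documents do not describe staffing, so a site without a masked person free for the two added tests would have to arrange one. Bias from participants' own knowledge of their assignment remains.

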6.8 Exam Requirements

The following are examinations to be performed at the times indicated in Appendix 1.

1. Informed Consent and Eligibility Criteria Review
2. Demographics and Participant Contact Information Review
3. Medical/Ophthalmic History Review (carried over from NTMT-01 or NTMT-02)
 - Adverse events noted during the NTMT-02 and NTMT-01 study period and up to the first Extension Study visit will be added as Medical/Ophthalmic History as applicable.
4. Adverse Event Assessment (from the date of the NTMT-01/02 Extension Study consent)
5. Concomitant Medications
6. Complete Ophthalmic Examination including:
 - Manifest refraction
 - BCVA (This test will be performed by a masked certified technician)
 - Goldmann applanation tonometry
 - Slit lamp biomicroscopy
 - Dilated fundus examination
 - Implant site clinical examination
7. Ophthalmic Assessments including:
 - Microperimetry
 - Spectral Domain Optical Coherence Tomography (SD-OCT)
 - Fundus Autofluorescence imaging
 - Digital Color Fundus photographs

- Adaptive Optics Scanning Laser Ophthalmoscopy (AOSLO), in selected participants
 - Participants who underwent AOSLO for NTMT-02 will undergo a separate consent process at the AOSLO Center if they agree to continue participating.

8. Reading Speed –NTMT-02 (Cohort 2) participants only

- Monocular and binocular reading speed will be assessed using IReST cards. Reading speed will be used to document the participant's functional status with an important everyday visual task.

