Cohort 2: The following efficacy outcomes as outlined in the NTMT-02 Protocol will continue to be analyzed to investigate the efficacy of Ciliary Neurotrophic Factor (CNTF) produced by NT-501 (all changes relative to NTMT-02 baseline measurements):

- Change in the ellipsoid zone (area of IS/OS loss) from baseline to Months 36, 48, 60 and 72.
- Change in retinal sensitivity (dB) as measured by microperimetry from baseline to Months 36, 48, 60 and 72.
- Proportion of study eyes with a 35% or more increase from baseline in the ellipsoid zone (area of IS/OS loss) at Months 36, 48, 60 and 72.
- Change in BCVA from baseline to Months 36, 48, 60 and 72.
- Proportion of study eyes with 15 or more letter loss from baseline in BCVA at Months 36, 48, 60 and 72.
- Proportion of study eyes with 10 or more letter loss from baseline in BCVA at Months 36, 48, 60 and 72.
- Change in reading speed from baseline to Months 36, 48, 60 and 72.

Assessment/Examination Schedule

	VISIT 1 (+/- 1 month)	VISIT 2 (+/- 1 month)	VISIT 3 (+/- 1 month)	VISIT 4 (+/- 1 month)
VISITS ARE SCHEDULED FROM THE DATE OF THE NTMT-01 OR NTMT-02 SURGERY				
GENERAL ASSESSMENTS				
NTMT-01/02 Extension Study Consent	X			
Review Eligibility Criteria	X			
Review Demographics and Participant Contact Information	X			
Update Medical & Ophthalmic History from NTMT-01 and NTMT-02 -This will include AEs collected during NTMT-01 and NTMT-02 and up to Visit 1 of the Extension Study as applicable. Any events between the last NTMT-01 or NTMT-02 visit will be recorded here.	X			
AE Assessment – starting from date of NTMT-01/02E Consent		X	X	X
Concomitant Medications – continue from NTMT-01 and NTMT-02	X	X	X	X
Reading Speed* *Completed for NTMT-02 (Cohort 2) participants only	X*	X*	X*	X*
VISUAL SYSTEM EXAMS: UN-DILATED				
Manifest Refraction	X	X	X	X
Best Corrected Visual Acuity	X	X	X	X
Applanation Tonometry (Goldmann applanation tonometer)	X	X	X	X
Microperimetry	X	X	X	X
VISUAL SYSTEM EXAMS: DILATED				
Slit lamp Biomicroscopy	X	X	X	X
Dilated Fundus Examination	X	X	X	X
Implant Site Clinical Examination	X	X	X	X
SD-OCT	X	X	X	X
Fundus Autofluorescence Imaging	X	X	X	X
Digital Color Fundus Photographs	X	X	X	X
AOSLO (for participants enrolled at NTMT-02 baseline) Requires separate consent at AOSLO Center	X**	X**	X**	X**

Table of Contents

1	Précis.....	1
2	Background and Rationale	2
3	Scientific Rationale.....	5
	3.1 Encapsulated Cell Technology (ECT)	5
4	Study Objectives	6

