- To investigate long term safety and efficacy of the NT-501 implant in participants previously enrolled in the NTMT-01 and NTMT-02 protocols.
- To investigate the change in the ellipsoid zone (area of [inner/outer segment] IS/OS loss) in participants previously enrolled in the NTMT-01 and NTMT-02 protocols, as measured by en face imaging by spectral domain optical coherence tomography (SD-OCT) in study eye(s).

5 Study Design and Methods

This is a prospective, multi-center, single-masked, sham-controlled follow-up study of the 7 participants that have completed 60 months of follow up in the open label NTMT-01 study (Cohort 1) and the 66 participants who completed 24 months of follow up in the NTMT-02 study (Cohort 2). All participants will be followed for an additional 48 months. Appendix 1 presents the scheduled examinations during the extended 48 month follow up period.

In the event that the NTMT-02 study is positive, Cohort 2 participants who received sham only may be eligible for active treatment in the control/non-treated eye.

6 Study Conduct

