6.1.3 Safety Outcomes

The following ocular events (regardless of attribution) will be considered safety outcomes for both Cohorts if they occur:

- Rejection or extrusion of the NT-501 device.
- Development of peri-implant fibrosis, which either blocks the visual axis of the implanted eye or affects the lens or retina (minor/moderate fibrosis around the implant and/or the attachment point is an expected possibility and will be considered safe on ocular function). Attention should focus on fibrosis that may detach the retina.
- Development of choroidal or retinal neovascularization in the study eye.
- Adverse events affecting ocular function, which are different from those expected in the normal course of MacTel, which are potentially related to the surgical procedure, implant or CNTF including:
 - Endophthalmitis
 - Vitreal inflammation
 - Tractional retinal detachment

- Sectorial lens opacification
- Intraocular hemorrhage
- High or low Intraocular pressures
- Dry eye
- Self-reported change in dark adaptation
- Miosis
- Persistent chemosis
- Scleral leak

All adverse events (AEs) will be captured from the date of the Extension Study Consent whether or not considered to be related to the surgical procedure, NT-501 device, or CNTF. All adverse events occurring between the final NTMT-01 or NTMT-02 study visit will be considered part of the participants' Medical and/or Ophthalmic History.

An attempt will be made to differentiate between treatment-related AEs and AEs considered to be part of the normal progression of the disease. In addition, for treatment-related AEs, an attempt will be made to differentiate those the Investigator believes are due to the procedure, NT-501 device, or CNTF.

Analysis of safety events will be conducted separately for each Cohort.

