6.9 Study Visit Procedures

Visits will occur annually for a total of 4 years following the below schedule with visit windows of +/- 1 month.

	Visit 1	Visit 2	Visit 3	Visit 4
Cohort 1	72 Months	84 Months	96 Months	108 Months
Cohort 2	36 Months	48 Months	60 Months	72 Months

The following study procedures will be completed only at Visit 1:

- If the participant agrees to continue in the Extension study, the Principal Investigator or appropriate designee will obtain the participant's consent
- Eligibility Criteria Review
- Demographics and Participant Contact Information Review
- Medical/Ophthalmic History Review (carried over from NTMT-01 or NTMT-02 study, including any AE's that have occurred since the last participant visit)

The following study procedures will be completed bilaterally at all visits for all participants unless otherwise noted:

- Adverse Event Assessment (only at Visits 2, 3, and 4)
- Concomitant Medications
- Manifest refraction
- Best Corrected Visual Acuity
- Goldmann applanation tonometry
- Microperimetry
- Slit lamp biomicroscopy

- Dilated fundus examination
- Implant site clinical examination
- SD-OCT
- Fundus Autofluorescence imaging
- Digital Color Fundus photographs
- Reading Speed – (Cohort 2 participants only)
- Adaptive Optics Scanning Laser Ophthalmoscopy (AOSLO), in selected participants

Participants who underwent AOSLO for NTMT-02 will undergo a separate consent process at the AOSLO Center if they agree to continue participating

7 Monitoring Participants and Criteria for Withdrawal

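### The AE and SAE tables described in 8.4 and 8.5 contain no general events from the interval between the last parent-study visit and extension consent, nominally 12 of the 48 extension months

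*Combined protocol and SAP*

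**What the plan says.** The first objective in section 4 is "To investigate long term safety and efficacy of the NT-501 implant in participants previously enrolled in the NTMT-01 and NTMT-02 protocols". Section 5 says that Cohort 1 has completed 60 months and Cohort 2 has completed 24 months of parent follow-up, and adds: "All participants will be followed for an additional 48 months".

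Section 6.9 lists consent among the procedures done only at Visit 1, which falls at Month 72 (Cohort 1) or Month 36 (Cohort 2), with a window of one month either side. The AE assessment is scheduled for the second, third and fourth visits, not the first.

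On when recording starts, section 6.1.3 says "All adverse events (AEs) will be captured from the date of the Extension Study Consent", and section 7.2 gives the same start and ends recording at the last visit.

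On earlier events:
- Section 6.1.3: "All adverse events occurring between the final NTMT-01 or NTMT-02 study visit will be considered part of the" participant's history, medical or ophthalmic. The sentence names only one end of the interval.
- Section 6.8 supplies the other end: such events "up to the first Extension Study visit will be added as Medical/Ophthalmic History as applicable".
- Section 6.9 has the Visit 1 history review take in AEs "that have occurred since the last participant visit".
- The schedules in the Study Summary and Appendix 1 put AEs "up to Visit 1 of the Extension Study as applicable" on the history line.

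Section 8.4 bases the long-term safety assessment on AEs, SAEs and the 6.1.3 outcomes, in descriptive form. Section 8.5 adds summaries by severity and by relatedness to the implant or its surgery. Neither section mentions history entries or data carried in from the parent studies.

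**The concern.** Long-term safety is in the first-named objective, yet the rules for recording and filing events, followed exactly, leave the first part of the extension out of the general AE and SAE tables. Nothing in 8.4 or 8.5 tells a reader that this period is absent. Efficacy change, by contrast, is measured from the parent baseline and so runs through the interval.

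Grading is a second difficulty. Section 7.4 requires severity and causality when an AE is reported. No passage asks for either on a history entry. Even if someone later decided to add the interval events to the tables, the severity and relatedness summaries in 8.5 could not be built from what the protocol requires to be recorded.

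**Working it through.** **Inputs.** Parent follow-up of 60 and 24 months, and an extension of 48 months (section 5). Visits at Months 72, 84, 96, 108 and at Months 36, 48, 60, 72, each within one month (section 6.9). Seven and 66 participants (section 8.3).

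**Reproducing the plan's figure.** Extension length = Visit 4 month − last parent month. Cohort 1: 108 − 60 = 48. Cohort 2: 72 − 24 = 48. Both agree with section 5, so the stated 48 months begin at the last parent visit and not at extension consent.

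**Interval before consent.** Visit 1 month − last parent month. Cohort 1: 72 − 60 = 12. Cohort 2: 36 − 24 = 12. Share of the extension: 12/48 = 25.0%.

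**Effect of visit windows.**
- Visit 1 window only, with the last parent visit exactly at Month 24 or 60: 11 to 13 months; 11/48 = 22.9%, 13/48 = 27.1%.
- If the parent visit also had a one-month window (an assumption; the documents do not say): 10 to 14 months; 10/48 = 20.8%, 14/48 = 29.2%.

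**Prospective AE recording, Visit 1 to Visit 4.** 108 − 72 = 36 and 72 − 36 = 36 months. With both windows, 71 − 37 = 34 to 73 − 35 = 38 months for Cohort 2, and the same range for Cohort 1 (107 − 73 to 109 − 71).

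**Participant-years, assuming all enrol and complete** (N × months / 12):

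| | Extension | Before consent | Prospective |
|---|---|---|---|
| Cohort 1 (7) | 28 | 7 | 21 |
| Cohort 2 (66) | 264 | 66 | 198 |
| Total (73) | 292 | 73 | 219 |

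73/292 = 25%. Measured from surgery the interval is a smaller share: 12/108 = 11.1% for Cohort 1 and 12/72 = 16.7% for Cohort 2.

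**What this could mean in events.** The documents give no event rate. For an assumed annual risk r per participant, expected interval events = 73r and the chance of at least one = 1 − (1 − r)^73:

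| r (assumed) | Expected | Chance of at least one |
|---|---|---|
| 1% | 0.7 | 52% |
| 2% | 1.5 | 77% |
| 5% | 3.7 | 98% |
| 10% | 7.3 | >99.9% |

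**Tracing an event.** Take a non-ocular SAE in a Cohort 2 participant at Month 30. It precedes consent, so 6.1.3 and 7.2 do not record it as an extension AE. Sections 6.8 and 6.9 and both schedules file it as history at Month 36. Sections 8.4 and 8.5 do not draw on history. A worsening after consent could be reported as an AE under 7.3, but the original onset would still be missing from the tables.

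**The case against.** The strongest reply is that this is a consistent and disclosed choice. AE capture starts at consent, earlier events are logged as history in every place that mentions them, and nothing is discarded. The 6.8 sentence also sends parent-study AEs to history, so filing there is a carry-over log and does not by itself cancel AE status. That is fair. The exclusion comes from the consent start date, combined with analysis sections that do not look at history. It remains that the tables, as described, omit the interval and do not say so.

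Three stronger readings are tempting, and the documents do not support them.

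- *A reader might infer that serious interval events escape expedited reporting.* The 24-hour duty in 7.4 applies to any SAE and runs from when the investigator first learns of it, with no limit on onset. The loss shown is in tabulation and grading.
- *A reader might infer that filing these events as history contradicts 7.3.* That section uses two anchors. Its AE definition looks to the start of study treatment, which would place interval events after the anchor. Its guidance on exacerbations looks to the start of the study and to baseline, under which history filing is arguably consistent. The anchors need reconciling, but neither settles the matter.
- *A reader might infer that implant-specific harms are missing too.* Section 6.1.3 introduces its ocular list with "The following ocular events (regardless of attribution) will be considered safety outcomes for both Cohorts if they occur" and gives no start date. Such events in the interval may therefore be counted under 8.4. The certain gap is in general AEs and SAEs.

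The parent protocols and the Safety Plan (7.1) are not in the documents, and either may cover the interval. What the history forms collect cannot be seen either.

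**Conclusion.** The concern holds for the tables as sections 8.4 and 8.5 describe them: no general AEs or SAEs from nominally 12 of the 48 extension months (25%; 11 to 13 months with the Visit 1 window). The 73 of 292 participant-years rest on full enrolment and completion, a last parent visit at Month 24 or 60, and consent at Visit 1 as scheduled. Earlier consent would shorten the interval, and the 6.8 history rule, which runs to Visit 1, would then overlap with AE capture. The figure is follow-up time, not a count of lost events. It is not all implant exposure, because some Cohort 2 participants received sham only.

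A biased incidence estimate is not shown, since the safety analysis is descriptive. The defect is an unstated, incomplete capture window, with no grading required for the events that fall outside it. It should be fixed because it bears on the first-named objective and the events are already being asked for.

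**What to change.** 1. At Visit 1, for each event with onset since the last parent visit (already requested in 6.9), record onset date, seriousness, severity and causality, with the flag *onset before extension consent*.
2. Amend 6.1.3, 6.8, 6.9, 7.2 and both schedules together, so that each names both ends of the interval. For 7.2, for example: *Prospective AE recording runs from extension consent to the final visit. Events that began after the final NTMT-01 or NTMT-02 visit but before consent are entered at Visit 1, graded and flagged.*
3. Give the ocular outcomes in 6.1.3 a start date.
4. In 8.4 and 8.5, state the AE capture window and tabulate the flagged events as a subtotal separate from prospectively collected AEs. Count each event once if a parent study already reported it.
5. Confirm that the existing 7.4 clock, from when the investigator first learns of the event, applies to interval SAEs.
6. Reconcile the two anchors in 7.3, and check that the Safety Plan agrees.

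The cost is protocol and eCRF wording, plus grading and causality assessment at Visit 1. The drawback is about 12 months of recall and judgement in retrospect, so these entries will be weaker than prospective ones. The flag and the separate subtotal make that visible. If retrospective grading is judged not worthwhile, items 3 and 4 could be limited to stating the capture window and the start date. That would disclose the gap without filling it.
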